## Study Objectives

**Aim 1:** Examine the effectiveness of CR + tDCS to improve behavioral and neurophysiological measures of **cognitive control** among smokers with schizophrenia. Using a 2 X 2 factorial design (n=20 per group) we will examine main and interactive effects of CR and tDCS on multiple measures of cognitive control. Hypothesis: Combined CR + tDCS will result in greater improvement in MATRICS measures of cognitive control, as well as continuous performance task (CPT) relative to the other groups (CR + sham tDCS, AC + tDCS, AC + sham tDCS).

**Aim 2:** Determine the effectiveness of CR + tDCS to attenuate **reactivity to smoking stimuli** among smokers with schizophrenia. Hypothesis: CR + tDCS will lead to greater reductions in cue-induced craving, and improved reaction time and ERP measures of attentional bias relative to the other groups (CR + sham tDCS, AC + tDCS, AC + sham tDCS).

**Aim 3:** Examine if cognitive control enhancement (Aim 1) and/or changes in reactivity to smoking-related stimuli (Aim 2) predict reductions in measures of **actual smoking behavior**. Hypothesis: Enhanced cognitive control and attenuation of reactivity to smoking stimuli will be directly

related to reductions in smoking topography (i.e., Latency to light, puff volume, and number of puffs) within the CR + tDCS group.

**Secondary Aim:** To inform future clinical research, we will also explore whether changes in cognitive control and smoking reactivity measures are associated with changes in **quit intention** and **confidence in quitting** from baseline assessment to end of study by training condition.

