## Procedures and protocol

Eligible participants will be invited to the Clinical Neurophysiology Research Lab for informed consent and further screening, including CO, Smoking and Medical history, PANSS, Intention to quit, Confidence in quitting, and hearing/vision testing to screen for sensory problems that may affect cognitive and/or EEG testing. After initial screening on Day 1, participants will be randomized. Randomization for the 4 groups will be stratified by current typical or atypical antipsychotic medication to control for the potential interaction of tDCS with medication class. A randomization assignment list will be generated for each category using a permuted 4 block design. Dropouts will be replaced. Participants will then be scheduled for two baseline testing sessions, completed the same week as initial screening. The first will utilize the MATRICS Clinical Consensus Battery (MCCB) for baseline testing of cognitive measures. Participants will perform form A of the MCCB at baseline, which includes composite scores for attention, processing speed, working memory, and reasoning/problem solving. Participants will also complete behavioral tests of cognitive control, cue reactivity and attentional bias during this visit. Participants will then complete a baseline EEG testing session on a separate visit in the same week. Electrophysiological measures of cognitive control will be examined using the 'AX'-type Continuous Performance Task (AX-CPT). Cue-induced craving and smoking topography will be assessed with a pictorial cue reactivity paradigm, and attentional bias will be measured using a modified stroop task. Following baseline testing (Week1), participants will return 5 days (M-F) for the next 2 weeks for cognitive training with CR / tDCS and will receive the same tDCS condition in each visit. In week 4, participants will perform follow-up testing using form B of the MCCB, behavioral tests of cognitive control, cue-reactivity, and attentional bias on the first day, and EEG testing on the second.

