## Data Analysis

Prior to hypothesis testing, descriptive statistics and graphic displays will identify outliers and missing data and guide the use of transformations and appropriate tests. Correlation and principal component analysis will identify any outcomes reflecting the same underlying construct, and representative measures will be selected if necessary. We will use 2x2 ANOVA to assess the effects of tDCS (vs sham) and CR (vs AC) on pre-post change scores for all dependent variables. Should baseline differences be identified, post-training scores will be used as dependent variables, and baseline (pre-training) scores will be included as covariates in the analysis.

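### Baseline adjustment depends on undefined 'baseline differences'; ANCOVA for every outcome would use the same data and gain power unless the pre-post correlation is high

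*Combined protocol and SAP*

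**What the plan says.** Study Objectives gives the design: "Using a 2 X 2 factorial design (n=20 per group) we will examine main and interactive effects of CR and tDCS". That is 80 participants, 40 v 40 for each main effect and 20 v 20 for a comparison of two cells.

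Data Analysis sets the default as "2x2 ANOVA to assess the effects of tDCS (vs sham) and CR (vs AC) on pre-post change scores for all dependent variables". It then makes an exception: "Should baseline differences be identified, post-training scores will be used as dependent variables", with the pre-training score added as a covariate. It does not say how a difference is identified, on which contrast, at what threshold, or whether the switch applies to one outcome or to all. The nearest guidance is the opening statement that "descriptive statistics and graphic displays will identify outliers and missing data and guide the use of transformations and appropriate tests".

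Two parts of Procedures and protocol bear on the choice. For the cognitive battery, "Participants will perform form A of the MCCB at baseline", and Week 4 has "follow-up testing using form B of the MCCB". Randomisation is "stratified by current typical or atypical antipsychotic medication to control for the potential interaction of tDCS with medication class", but Data Analysis does not mention antipsychotic class.

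**The concern.** The groups are randomised, so a baseline difference is mainly chance, and whether one is noticed is a poor basis for choosing the model. Three things follow.

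- **Precision.** A change score fixes the slope on baseline at 1; ANCOVA estimates it. When the true slope is below 1, the change score carries avoidable noise, and 20 per group leaves little to spare. A slope of 1 is a strong assumption for the cognitive battery, where the form differs between visits.
- **Chance imbalance that is not flagged.** With equal SDs, the change score over-corrects an observed imbalance by (1 - rho) times its size. ANCOVA does not.
- **Reproducibility.** With no stated trigger, the model for each outcome is settled after the data are seen.

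A secondary point is that the stratification factor, chosen because of a possible interaction with tDCS, is neither adjusted for nor examined. This is an omission, not a bias.

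**Working it through.** **Inputs from the documents.** Four groups of 20; one baseline and one Week 4 measurement; change-score default; conditional ANCOVA. The plan states no power figure, so there is none to reproduce.

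**Assumptions.** Two-sided alpha 0.05; a tDCS main effect of 0.5 SD of the Week 4 score; normal outcomes; 20 completers per cell; equal SDs unless stated; rho from 0.3 to 0.9.

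**Step 1: variance.** The residual variance is 2·SD²·(1 - rho) for the change score and SD²·(1 - rho²) for ANCOVA. The ratio, ANCOVA over change score, is (1 + rho)/2 whatever the effect size. To match ANCOVA with 20 per cell, change scores need 20 × 2/(1 + rho) per cell.

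| rho | Variance ratio | Change-score n per cell to match 20 |
|---|---|---|
| 0.3 | 0.65 | 30.8 |
| 0.5 | 0.75 | 26.7 |
| 0.7 | 0.85 | 23.5 |
| 0.8 | 0.90 | 22.2 |
| 0.9 | 0.95 | 21.1 |

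Estimating the slope inflates the ANCOVA variance by about 1 + 1/74 = 1.0135. Break-even is therefore at rho = 2/1.0135 - 1, about 0.97.

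**Step 2: power of the planned rule.** Because the trigger is undefined, four readings were simulated (100,000 trials per setting). They flag from 5% of outcomes (omnibus F, p<0.05) to 60% (any of three standardised differences above 0.25). The table takes any of the three baseline effects at p<0.05, which flags 14%. The last column gives ANCOVA's gain across all four readings.

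| rho | Planned rule | Always ANCOVA | Gain over four readings (points) |
|---|---|---|---|
| 0.3 | 48% | 63% | 7-16 |
| 0.5 | 62% | 72% | 5-11 |
| 0.7 | 82% | 87% | 2-5 |
| 0.8 | 94% | 95% | 0.6-1.7 |
| 0.9 | 99.9% | 99.9% | 0 |

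For a single 20 v 20 cell comparison (normal approximation), change score to ANCOVA is 27% to 38%, 35% to 45%, 53% to 60%, 71% to 75% and 94% to 95% at the same rho values.

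**Step 3: unequal SDs.** Let k be baseline SD over Week 4 SD. In Week 4 variance units the two variances are 1 + k² - 2k·rho and 1 - rho², so they differ by (k - rho)², which is never negative. The gain vanishes when rho is close to k. With k = 1.2, planned v ANCOVA power is 74% v 87% at rho 0.7 and 88% v 95% at rho 0.8. With k = 0.8 the two agree within 0.3 points at those values.

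**Step 4: type I error.** With any of the four triggers fixed in advance, the planned rule has type I error 0.039-0.049. If the analyst instead kept the smaller of the two p-values, it would be 7.8%, 7.3%, 6.7% and 6.0% at rho 0.3, 0.5, 0.7 and 0.9.

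**Step 5: imbalance that escapes the trigger.** For a given contrast, about 24% of outcomes are unflagged but have a baseline |t| between 1 and 2, with a mean imbalance of 0.31 SD. The change score is then off by (1 - rho) × 0.31: about 0.22 SD at rho 0.3, 0.09 at 0.7 and 0.03 at 0.9. Its conditional type I error falls from about 0.08 at rho 0.3 to between 0.05 and 0.06 at rho 0.9; ANCOVA stays near 0.05. In the roughly 62% with |t| below 1, the change-score test is conservative (0.023-0.046), which is why the overall rate is sound.

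**Step 6: the stratum.** A stable class effect cancels from a change score, and adding class to ANCOVA then gains 0-3 points of power. With 73 residual degrees of freedom and rho 0.3-0.7, a tDCS-by-class difference has 80% power only at about 0.9-1.2 SD if classes split 50:50, or 1.1-1.5 SD if 20:80.

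**The case against.** The best defence is that the default is valid: under randomisation it is unbiased, and with a fixed trigger it keeps its type I error. Preferring ANCOVA is then a matter of efficiency, and its size rests on assumed values. That is right about validity, but it does not supply the missing trigger, and the reassurance on type I error holds only for a trigger fixed in advance.

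Second, not every baseline difference need be chance. Procedures and protocol randomises before the baseline test sessions and replaces dropouts, so the analysed set may differ from the randomised set. If a real and stable difference arose, with equal SDs ANCOVA would leave (1 - rho) of it and the change score would remove it. This is a fair caution, but it does not support the planned rule, which moves to ANCOVA precisely when a difference is seen.

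Third, the aims compare the combined group with each other group, whereas the main power table is for a main effect. The 20 v 20 figures also favour ANCOVA, and the zero gain at rho 0.9 in that table is a power ceiling.

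Fourth, puff counts, latency within a 10-minute window and quit intention may not suit a linear model. The screening for transformations and suitable tests should stay, and the simulations cover normal outcomes only.

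Fifth, the change of test form is weak evidence. A form difference common to all groups cancels, and the argument does not depend on it.

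**Conclusion.** The concern holds. The switch to baseline adjustment has no criterion, and ANCOVA for every outcome would use data already collected. Under the stated assumptions the planned rule gives up about 7-16 points of main-effect power at rho 0.3, 5-11 at 0.5 and 2-5 at 0.7, with under two points at stake from about 0.8 when the SDs are similar. Rho, effect size, alpha and trigger are all assumed; the variance ratio (1 + rho)/2 needs only equal SDs.

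The harm is lost precision and a rule that cannot be reproduced, not bias. Inflated false positives, to about 6-8%, would arise only if the open trigger were used to choose the better result. The rule needs repair even if rho is high. The sponsor should make this change, but the trial is not invalid without it. The stratum point is minor.

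**What to change.** Keep the screening text in Data Analysis and replace its last two sentences with wording such as:

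> For every outcome the Week 4 score is analysed by ANCOVA with CR, tDCS, CR x tDCS, the baseline score and the antipsychotic randomisation stratum as assigned, whether or not baseline differences are seen.

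Delete the baseline-difference trigger. Where an outcome is transformed, apply the transformation at both visits. Where a linear model does not suit an outcome, name the alternative and keep the baseline score in it.

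Add a tDCS-by-stratum term as a sensitivity analysis, reported as an estimate with a 95% confidence interval because its power is low.

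**Cost.** SAP wording only and no new data. Baseline and stratum use two degrees of freedom out of 80 - 4 = 76. The worst simulated loss of power for ANCOVA was 0.3 points, at rho 0.8 with baseline SD 20% below Week 4.
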